Proposal Title:

A Comparative Study on Functional Vision and Digital Device Usage in Astigmatic Patients: DAILIES TOTAL1 Toric Contact Lenses vs. Spherical Equivalent Contact Lenses in Asian Eyes

[name], Principal Researcher, Mopsy Research

DATE: 20 DEC 2023

Background:

In today's digital age, individuals spend a significant amount of time using digital devices ^[1]. This is notably challenging for individuals with astigmatism, a condition that can impair visual acuity when using these devices ^[2]. Despite the prevalence of astigmatism, toric contact lens technology, which can potentially improve visual acuity for these individuals, remains underused ^{[3][4]}. Many eye care practitioners opt for spherical lenses due to perceived complexities of fitting and considerations of cost-effectiveness ^{[5][6]}.

DAILIES TOTAL1[®] for Astigmatism contact lenses, the first and only daily disposable Water Gradient toric contact lenses, can potentially address this issue. These lenses represent a significant innovation in toric contact lens technology, offering a unique combination of breathability and exceptional comfort. The lenses utilize Water Gradient Technology, creating a gradual transition in water content from the core to the surface of the lens, with the water content approaching 100% at the lens surface. This technology enables these lenses to offer a combination of high breathability and exceptional comfort.

Unmet Medical Need:

Although toric lenses, including DAILIES TOTAL1[®] for Astigmatism, have been shown to improve visual acuity in astigmatic patients, their impact on real-world visual performance, particularly when using digital devices, is less understood ^[1]. Additionally, while many practitioners gravitate towards spherical lenses, astigmatic patients could greatly benefit from the comfort and visual acuity provided by DAILIES TOTAL1[®] for Astigmatism contact lenses.

Gaining insights into the real-world visual performance of astigmatic patients when using DAILIES TOTAL1[®] for Astigmatism contact lenses could provide valuable information to eye care practitioners and patients. This could potentially encourage the broader adoption of DAILIES TOTAL1[®] for Astigmatism contact lenses, improving the visual experience for astigmatic patients and addressing an unmet medical need.

Scientific Rationale:

Previous clinical studies have demonstrated the benefits of toric contact lenses in improving visual acuity in astigmatic patients[5]. However, these studies primarily used traditional high-contrast, high-luminance visual acuity testing, which may not accurately reflect the visual demands of real-world tasks, especially those involving digital devices ^{[7][8]}.

DAILIES TOTAL1[®] for Astigmatism contact lenses stand out due to their unique Water Gradient Technology and Precision Balance 8|4[®] Lens Design. The gradual transition in water content from the core to the surface of the lens, with the water content approaching 100% at the lens surface, enables a combination of high breathability and exceptional comfort. The lens design ensures a quick and stable fit, with 99% first-lens fit success. Additionally, these lenses feature SmarTears[®] Technology, which releases an ingredient found naturally in tears to stabilize the lipid layer of the tear film, further promoting comfort for the wearer.

This study seeks to extend previous findings by evaluating the impact of DAILIES TOTAL1[®] for Astigmatism Contact Lenses on subjective and objective visual performance outcomes in astigmatic patients using digital devices ^[9]. This will involve the use of advanced digital real-world and patient-reported outcome tools, providing a comprehensive evaluation of vision beyond acuity alone. The goal is to ascertain whether the unique benefits of DAILIES TOTAL1[®] for Astigmatism Contact Lenses translate to improved functional vision and overall satisfaction for astigmatic patients.

Objective:

This study aims to assess the impact of DAILIES TOTAL1[®] for Astigmatism Contact Lenses on the functional vision of astigmatic patients as compared to DAILIES TOTAL1[®] Spherical Contact Lenses, using digital real-world and patient-reported outcome tools in Asian Eyes.

Hypothesis:

DAILIES TOTAL1[®] for Astigmatism Contact Lenses will improve both subjective and objective visual performance in astigmatic patients using digital devices compared to DAILIES TOTAL1[®] Spherical Contact Lenses in Asian Eyes.

Methodology

Recruitment and Enrolment

The study will involve adult participants aged between 18 and 39 years with -0.75 to -1.50 D of astigmatism. Potential participants will initially be screened for study eligibility by phone or in-person discussion. All subjects will consent before enrolment in the study.

Inclusion Criteria:

1. Asian (self-report and be confirmed by PI observation)
2. Ages between 18 and 39 years
3. Vertexed corrected sphere power between -0.50 and -6.00 D
4. Vertexed refractive cylinder power between -0.75 and -1.50 D
5. Best corrected acuity of 20/25 or better in each eye
6. Habitual soft contact lens wearers at least 6 months (who should be successfully fitted with both DT1 Spherical and Toric contact lens)

Exclusion Criteria:

1. History of ocular pathology or surgery
2. Active ocular infection or clinically significant ocular inflammation
3. Any significant binocular vision abnormalities
4. Wearers of gas-permeable lenses for at least 3 months prior to the study
5. Pregnant or lactating individuals (by self-report)

Study Design:

This study will follow a double-masked randomized crossover design^[10], where participants will be fitted with DAILIES TOTAL1® for Astigmatism and DAILIES TOTAL1® Spherical Contact Lenses in a randomized order. Each participant will use both types of lenses over different periods. The study will be composed of five visits:

	Visit 1 (Baseline and fitting for lens 1)	Visit 2 (D2±1 lens 1 follow-up)	Visit 3 (D4 ±1 Outcomes for lens 1 and fitting for lens 2)	Visit 4 (D6 ±1 lens 2 follow-up)	Visit 5 (D8 ±1 Outcomes for lens 2)
Inclusion/Exclusion Criteria Screening	X				
Fitting	X		X		
NAVQ test	X		X		X
high-contrast, high-luminance and low-contrast, high-luminance visual acuity at 40 cm and 6 m (logMAR) by EyeChart PRO and E-ETDRS (NIDEK SC-2000)			X		X
MNREAD reading performance test	X		X		X
Slit lamp assessment & over-refraction	X	X	X	X	X

The assessments will be conducted following the sequence in this table

Timeline:

Each lens pair will be measured three times: Fitting, follow-up and outcome measurement

Visit 1 - Baseline Evaluation and Fitting for Lens 1

1. Obtain informed consent.
2. Collect subject demographics, medical and ocular health, and information on concomitant medications.
3. Measure binocular near logMAR visual acuity with the participant's habitual correction.
4. Administer the Near Activity Visual Questionnaire (NAVQ) to gauge the participant's subjective experience of near vision function. ^[11]
5. Evaluate the participant's reading performance, speed, and functionality with the MNREAD app. This will involve:
 - i. Reading Acuity: Determine the smallest print size so that the participant can accurately read without making significant errors. The app will present sentences in various print sizes, starting from larger to smaller.
 - ii. Critical Print Size: Identify the smallest print size that the participant can read at their fastest speed. This will be determined by observing the smallest print size read at the maximum speed by the participant.
 - iii. Maximum Reading Speed: Assess by presenting sentences in a print size comfortable for the participant, then timing how long it takes for them to read these sentences. The reading speed will be computed in words per minute.
 - iv. Reading Accessibility Index: Calculate this single-value measure, which represents a person's visual access to commonly encountered printed material, using data from the previous steps.
6. Conduct manifest refraction using maximum plus to best visual acuity.
7. Assess accommodation and binocular vision.
8. Measure pupil size in dim and bright light settings.
9. Complete an anterior segment slit lamp examination.
10. After confirming eligibility, randomize and fit the subject with the first pair of contact lenses.
11. Allow the contact lenses to settle for 10 minutes before evaluating the fit.
12. Perform an over-refraction and adjust the lens power if necessary.

Visit 2 - Contact Lens Follow-up 1

1. Assess the subject who should be wearing the assigned study contact lenses for at least 2 hours before the appointment.
2. Perform an over-refraction and adjust the lens power if necessary.
3. Conduct a slit lamp examination including ocular surface evaluation with sodium fluorescein after the contact lenses are removed.

Visit 3 - Outcome Measures for Lens 1 and Fitting for Lens 2

1. Have the subject report to the visit wearing their assigned study contact lenses for at least 2 hours before their appointment.
2. Administer the NAVQ.
3. Conduct high-contrast, high-luminance visual acuity at 40 cm & 6 m and low-contrast, high-luminance visual acuity at 6m
4. Evaluate the participant's reading performance, speed, and functionality with the MNREAD app

5. Perform a slit lamp examination including sodium fluorescein after removing the study contact lenses.
6. Fit the subject with the second pair of contact lenses based on the randomization schedule.
7. Allow the contact lenses to settle for 10 minutes before evaluating.
8. Perform an overrefraction and adjust the power of the alternate lenses if necessary.

Visits 4 and 5 - Contact Lens Follow-up 2 and Outcome Measures for Lens 2

1. Repeat the procedures from Visits 2 and 3 respectively for the second pair of lenses.

Randomization:

- Create a computer-generated list with 39 elements, each representing a type of lens (label "A" for DAILIES TOTAL1® for Astigmatism and "B" for DAILIES TOTAL1® Spherical Contact Lenses).
- Shuffle the elements of the list to ensure random assignment.
- Attach a coded sticker to each lens' blister packaging, corresponding to the codes in the computer-generated list.

Note: Only a designated unmasked examiner, who does not interact directly with the participants or influence the data collection, interpretation, or analysis, will have access to the decoding key for these stickers.

Visit 1:

- After confirming eligibility, the unmasked examiner consults the randomization list and selects the appropriately coded package for the participant.
- The unmasked examiner hands off the coded package to the masked examiner.
- The masked examiner fits the subject with the first pair of lenses, without knowing the type of lens they are administering.

Visit 3:

- Repeat the process from Visit 1: the unmasked examiner, based on the randomization list, selects the second pair of lenses for the participant.
- The unmasked examiner hands off the coded package to the masked examiner.
- The masked examiner fits the subject with the second pair of lenses, maintaining the blindness of the study.

End of Study:

- At the end of the study, the unmasked examiner references the coding key to reveal the order in which the lenses were administered to each participant, allowing the research team to analyze the results accordingly.
- This point form process ensures a robust double-blind crossover design, where the participants and the majority of the research team are not aware of the lens type being used at any point, reducing potential biases.

Endpoints:

Primary Endpoints:

1. Evaluate near (40cm) high-contrast visual acuity in logMAR by i-Pad-based applications – EyeChart PRO

Secondary Endpoints:

1. Evaluate participant's reading acuity, critical print size, maximum reading speed, and reading accessibility index using the MNREAD app. Specifically:
 - i. Reading Acuity: Identify the smallest print size that can be accurately read by the participant without significant errors. This is done by presenting sentences in decreasing print sizes.
 - ii. Critical Print Size: Determine the smallest print size that the participant can read at their fastest reading speed.
 - iii. Maximum Reading Speed: Measure by timing how long the participant takes to read sentences presented in a comfortable print size. The speed is calculated as words per minute.
 - iv. Reading Accessibility Index: Compute this single-value metric, indicative of a person's visual access to commonly encountered printed text, using data from the previous steps.
2. Evaluate the near visual function with the Near Activity Visual Questionnaire
3. Distance high-low contrast visual acuity in logMAR by using E-ETDRS (NIDEK SC-2000)

Sample size justification

1. The sample size for this study was calculated based on the results of a similar study [12] that assessed improvements in near high- and low-contrast visual acuity among astigmatic patients using toric contact lenses versus spherical contact lenses.
2. The primary endpoint for our study is like the referenced study, and we expect a 1-line treatment benefit (0.1 logMAR) as the minimum clinically important difference. The within-subject standard deviation of the outcome measure is also anticipated to be a line (0.1 logMAR) based on the referenced study.
3. To ensure adequate power for our study, set the significance level (α) at 0.05 (2-sided) and the power ($1-\beta$) at 0.80. Using these parameters and the formula for sample size calculation in a crossover design, we estimated a sample size of 35 participants.
4. A dropout rate of approximately 10%. To ensure sufficient power to detect a statistically and clinically significant difference in our primary outcome, we plan to enrol 39 participants in this clinical trial.

Statistical Analysis:

The treatment effects will be analyzed using the Grizzle model for the two-period, two-treatment crossover trial^[10]. The data will first be tested for the presence of a carryover effect according to the sequence of randomization, that is, sphere or toric, during the first period at the critical level of 0.10. Then, the treatment effect will be estimated using a linear mixed model in the presence of period and sequence effects to obtain unbiased effect sizes^[10].

Reference:

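### Does a hypothesis of both subjective and objective benefit need more than one primary endpoint on near acuity?

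*Combined protocol and SAP*

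**What the plan says.** The Hypothesis section predicts that the toric lens "will improve both subjective and objective visual performance in astigmatic patients using digital devices compared to" the spherical lens. The Scientific Rationale asks whether the lens's properties "translate to improved functional vision and overall satisfaction for astigmatic patients".

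Two background statements bear on the choice of primary:

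- Unmet Medical Need says that toric lenses, the study lens included, "have been shown to improve visual acuity in astigmatic patients, their impact on real-world visual performance, particularly when using digital devices, is less understood".
- Scientific Rationale says of earlier work that "these studies primarily used traditional high-contrast, high-luminance visual acuity testing, which may not accurately reflect the visual demands of real-world tasks".

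The endpoints are narrower than the hypothesis:

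- **Primary (Endpoints, Primary item 1):** "Evaluate near (40cm) high-contrast visual acuity in logMAR by i-Pad-based applications". The Visit 3 procedures (item 3) give the test condition: "Conduct high-contrast, high-luminance visual acuity at 40 cm".
- **Secondary:** the four MNREAD reading measures; NAVQ ("Evaluate the near visual function with the Near Activity Visual Questionnaire"); and distance acuity at high and low contrast.

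Sample size justification works only from acuity inputs: a 0.1 logMAR benefit, a within-subject SD of 0.1 logMAR, two-sided 5% and 80% power. It arrives at 35 evaluable and 39 enrolled, the aim being to "detect a statistically and clinically significant difference in our primary outcome". Statistical Analysis applies a Grizzle crossover approach and a linear mixed model to the treatment effects in general. It does not rank the endpoints beyond the primary and secondary labels.

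**The concern.** Read in sequence, the document appears to ask one question and size the trial for another. It says that an acuity benefit is known and that high-contrast acuity may miss what matters with digital devices. It then predicts gains in both subjective and objective performance, and makes high-contrast acuity the only primary. A significant primary would support better near acuity and nothing about how participants feel they see.

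Two things would be at stake. A report declaring the whole hypothesis confirmed would go beyond the one sized comparison. And a null NAVQ result would be hard to interpret, because the plan gives no effect, SD or power for it.

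**Working it through.** **1. The passages side by side**

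| Part of the hypothesis | Endpoint that addresses it | Status |
|---|---|---|
| Objective performance | Near high-contrast acuity on an iPad | Primary, sized |
| Objective performance | MNREAD measures, distance acuity | Secondary, not sized |
| Subjective performance, satisfaction | NAVQ (ten difficulty items and one satisfaction item, Appendix 2) | Secondary, not sized |

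Every part is measured, and NAVQ and MNREAD are repeated under each lens. Only the first row carries a sample-size claim.

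**2. How far the background undercuts the primary**

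The criticism is of traditional acuity testing, and the sentence is hedged (primarily, may not). The primary is measured at 40 cm on a tablet, which is closer to device use than a distance chart. No sentence says that near acuity on this app with this lens has been established. The sample-size section does cite a similar study of near acuity with toric and spherical lenses, but reports no result for this lens or app. So the primary is partly aligned with the digital-device question.

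**3. The plan's own figure**

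Inputs: effect 0.1 and within-subject SD 0.1 (Sample size justification, item 2); two-sided 5% and 80% power (item 3).

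- SD of the within-person difference = 0.1 × √2 = 0.141.
- Crossover formula: N = [0.141 × (1.960 + 0.842) / 0.1]² = 15.7, so 16; with the t distribution, 18.
- The stated 35 is not reproduced. It corresponds to an SD of the difference near 0.21, and a parallel two-group t-test comes close (2 × 17 = 34).
- The dropout step is reproduced: 35 / 0.9 = 38.9, so 39.

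The origin of 35 is a separate sample-size question. It says nothing about whether hypothesis and endpoint agree, and it carries no weight here.

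**4. What 35 evaluable participants give for NAVQ**

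The documents state no NAVQ effect or SD, so the effects below are assumptions, in units of the SD of the within-person difference. Power is from the noncentral t with 33 df and noncentrality = effect × √35, two-sided 5%.

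| Assumed NAVQ effect (SD) | Power |
|---|---|
| 0.2 | 21% |
| 0.3 | 41% |
| 0.4 | 63% |
| 0.5 | 82% |
| 0.6 | 93% |

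Power reaches 80% at 0.49 SD. Nothing in the documents says which row applies. NAVQ was not sized, but that does not show it to be undersized.

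**5. What a change would do**

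*Option A: narrow the hypothesis to near acuity and label the secondaries supportive.* The test, estimates, data and 5% level stay as they are. The endpoint labels already imply this reading.

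*Option B: claim both limbs only if acuity and NAVQ are each significant in favour of toric.* Because both must succeed, no alpha is split. Acuity power at 35 is 98% on the stated inputs and 82% if the SD of the difference is 0.2 (assumption). Joint power, taking the tests as independent:

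- stated acuity inputs: 0.982 × 0.819 = 80% (NAVQ 0.5 SD); 0.982 × 0.406 = 40% (NAVQ 0.3 SD);
- acuity SD of the difference 0.2: 0.819 × 0.819 = 67%; 0.819 × 0.406 = 33%. Simulation at correlation 0.5 gives about 71% and 38%.

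Option B rests a formal claim on an outcome with no stated inputs and no scoring rule for not-applicable answers. The cited source of NAVQ concerns presbyopia correction and participants here are 18 to 39, so scores may cluster near zero (an inference); power would then be lower than shown.

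**The case for a change.** The strongest case for a change is that the hypothesis says both, and nothing in the plan tells a reader which results would bear it out. A hypothesis may be broader than its primary, but a careful plan says which part the conclusion rests on. A sentence or two before unmasking would do that, at no cost in data or alpha, and would block a headline on subjective vision resting on an unsized secondary.

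Part of this stands. The wording is wider than the primary test, and the plan is silent on how the secondaries count. A report should rest its main conclusion on near acuity and present NAVQ and MNREAD as supportive, with estimates and intervals.

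It does not follow that the plan must change. Calling one outcome primary and the rest secondary already carries that meaning, and a single primary at two-sided 5% raises no multiplicity problem for the main conclusion. Narrowing the hypothesis would also leave half the complaint in place. It would tie the trial more tightly to acuity and further from the functional and patient-reported tools named in the Objective.

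**Conclusion.** No change follows. The mismatch in wording is real but minor: a two-part scientific hypothesis, one sized primary on near high-contrast acuity, and a subjective secondary with no stated inputs. Followed as written, the primary test remains valid and the secondary effects are still estimated.

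The default remedy would change no number. The alternative, a joint acuity and NAVQ claim, is a choice on which statisticians could reasonably differ. Its joint power at 35 runs from about 33% to 80% over the assumptions examined (NAVQ effect 0.3 or 0.5 SD, acuity SD of the difference 0.141 or 0.2, correlation 0).

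This conclusion assumes that the primary and secondary labels are read in the usual way and that the report keeps its main claim to near acuity. If the sponsor meant to make a formal claim of subjective benefit, NAVQ would need its own success rule and scoring rule; the plan does not state that intention.

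### Does inclusion criterion 6, which asks for a successful fit with both lenses, force exclusions after randomisation?

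*Combined protocol and SAP*

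**What the plan says.** Criterion 6 in the Inclusion Criteria asks for at least six months of habitual soft lens wear and adds, in brackets, "who should be successfully fitted with both DT1 Spherical and Toric contact lens". It does not say when or how a successful fit is judged.

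The order of events is clear and consistent:

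- **Recruitment and Enrolment:** "Potential participants will initially be screened for study eligibility by phone or in-person discussion".
- **Study Design, visit table:** the row "Inclusion/Exclusion Criteria Screening" is marked at Visit 1 only and stands above the fitting row.
- **Visit 1, step 10:** "After confirming eligibility, randomize and fit the subject with the first pair of contact lenses". Steps 1 to 9 include no study-lens fitting, and the fit is first evaluated at step 11.
- **Randomization, Visit 1:** "After confirming eligibility, the unmasked examiner consults the randomization list and selects the appropriately coded package for the participant".
- **Visit 3, step 6, after the lens 1 outcomes:** "Fit the subject with the second pair of contact lenses based on the randomization schedule".

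The Scientific Rationale describes the toric lens "with 99% first-lens fit success". The Statistical Analysis section says "the treatment effect will be estimated using a linear mixed model in the presence of period and sequence effects", without naming the participants who enter the model.

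**The concern.** An inclusion criterion should be checkable when eligibility is confirmed. If criterion 6 means that both study lenses have actually been fitted with success, neither half can be known before randomisation, and the second half is unknown until about day 4. Enforcing it would then be a post-randomisation exclusion. The comparison would be limited to people who succeed in both lenses, first-period outcomes already recorded could be discarded, and fit failures might go unreported. The lens that triggers the late exclusion would also depend on sequence: the spherical lens in toric-first participants and the toric lens in sphere-first participants. Fit failure bears on the study's own rationale too, since the Background names fitting difficulty as one reason practitioners choose spherical lenses. With no analysis population stated, the choice would be made after some outcomes were known.

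**Working it through.** **Can the criterion be checked before randomisation?** There are three readings.

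1. *Fitting history.* Visit 1 step 2 collects ocular health information before step 10, so history can be asked for there. The bracketed phrase is attached to a statement about existing wearers, which makes this reading natural.
2. *Expected suitability.* Step 6 (refraction) and step 9 (slit lamp) come before step 10 and inform a judgement that both lenses should fit. Criteria 3 and 4 already bound sphere and cylinder.
3. *Actual fit in the study.* This cannot be checked before step 10 and conflicts with the visit order.

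The problem arises only under the third reading, and only if someone also decides to remove participants. No section tells them to.

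**How many participants could be affected?** The inputs are 39 enrolled (Sample size justification) and 99% toric first-lens success (Scientific Rationale). The documents do not say whether that rate is per participant or per eye, so both are shown.

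- Per participant: 39 × 0.01 = 0.39 expected failures; chance of at least one = 1 − 0.99^39 = 0.324.
- Per eye, eyes assumed independent: 39 × (1 − 0.99²) = 39 × 0.0199 = 0.78 participants; chance of at least one = 1 − 0.99^78 = 0.543.
- Sphere-first participants who fail at Visit 3 with first-period data in hand, assuming 19 or 20 of 39 are sphere-first (the Randomization section does not state the split): 0.19 to 0.20 per participant, or 0.38 to 0.40 per eye.

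No spherical failure rate is given. With an assumed rate f, the share failing either lens is 1 − 0.99 × (1 − f):

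| Assumed f | Share failing either lens | Of 39 |
|---|---|---|
| 0% | 1.0% | 0.4 |
| 1% | 2.0% | 0.8 |
| 5% | 6.0% | 2.3 |

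This share is the same in both sequences if failure does not depend on period, so no imbalance between sequences is expected. First-lens success may also overstate final failure, because lens power can be adjusted at the fitting and follow-up visits.

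**Does power suffer?** The plan's inflation reproduces: 35 / 0.9 = 38.9, rounded up to 39. That leaves four places above the 35 required. The stated inputs (difference 0.1 logMAR, within-subject SD 0.1, so SD of the difference 0.1 × √2 = 0.141) do not themselves lead to 35. An SD of the difference of 0.2 comes closest, giving 34. Power is therefore shown for both, two-sided 0.05, t with n − 2 degrees of freedom:

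| n | SD of difference 0.141 | SD of difference 0.2 |
|---|---|---|
| 35 | 0.982 | 0.819 |
| 34 | 0.979 | 0.807 |

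Losing one participant costs about one percentage point at most.

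**Does the estimate move?** A sphere-first participant who cannot wear the toric lens has no toric outcome, so no within-subject difference exists to keep or discard. Retaining the single period in a mixed model adds only weak between-subject information. As a gauge, suppose one of 35 had no benefit and the other 34 averaged the planned 0.1 logMAR. The simple mean would be 0.1 × 34/35 = 0.097, and leaving that person out shifts it by 0.003 logMAR.

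**The case for a change.** The strongest case for acting is that the text does not choose between the readings, no step is labelled as a check of fitting history, and one sentence would settle it. Two people following the protocol could treat the same failed fit differently, and the choice would fall after first-period outcomes existed. The sequence facts behind this are right, and if actual fit is meant the criterion does conflict with the visit order.

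What stands is an ambiguity. The step to harm does not follow. Removal, discarded data and unreported failures are all possibilities that no section prescribes. The unstated analysis population affects every dropout equally and is not evidence about this criterion. A rule keeping every randomised participant in the model would not restore the missing comparison: the treatment contrast would still come almost entirely from people who wore both lenses. That is close to the population a crossover of two lenses is meant to describe. Replacing the phrase with a test against available lens parameters would be a different condition, and the documents do not give those parameters.

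**Conclusion.** No change follows. Criterion 6 is loosely worded, but it can be applied before randomisation as fitting history or expected suitability, and the plan does not call for excluding anyone after a failed fit. An analyst would ordinarily use the period data collected and report fit failures in the participant flow without being told to.

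On the documented toric rate, fewer than one of 39 participants is expected to be affected (0.39 or 0.78, depending on the unit of the 99%), and 0.2 to 0.4 would already have first-period outcomes. The effect on power and on the estimate is negligible. This rests on three assumptions: the 99% figure holds in this sample, the sequences are roughly balanced, and the spherical lens fails no more often than the assumed range of 0% to 5%, at whose upper end 2.3 participants would fail one lens or the other.

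### Does the visit table schedule a near (40 cm) low-contrast acuity test that the visit steps and endpoints leave out?

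*Combined protocol and SAP*

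**What the plan says.** The visit table under Study Design has one acuity row, ticked at Visits 3 and 5. It reads "high-contrast, high-luminance and low-contrast, high-luminance visual acuity at 40 cm and 6 m (logMAR) by EyeChart PRO" and goes on to name the E-ETDRS system as a second device.

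The numbered procedures for Visit 3 are more specific. Step 3 is: "Conduct high-contrast, high-luminance visual acuity at 40 cm & 6 m and low-contrast, high-luminance visual acuity at 6m". The section on Visits 4 and 5 carries this to the second lens: "Repeat the procedures from Visits 2 and 3 respectively for the second pair of lenses".

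Under Endpoints, the primary endpoint is "Evaluate near (40cm) high-contrast visual acuity in logMAR", taken with the iPad app. The third secondary endpoint is "Distance high-low contrast visual acuity in logMAR by using E-ETDRS". The other secondary endpoints are four MNREAD measures and the NAVQ.

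The Sample size justification rests on an earlier study that "assessed improvements in near high- and low-contrast visual acuity among astigmatic patients" and adds: "The primary endpoint for our study is like the referenced study".

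**The concern.** The table attaches both contrasts to both distances, while the steps drop low contrast at 40 cm. Nothing in the document ranks one above the other. If staff follow the steps, near low-contrast acuity is never measured with either study lens and cannot be recovered later. If they follow the table, the readings exist but belong to no endpoint, so any result from them would be unplanned.

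Two other places seem to favour the test. The Scientific Rationale doubts that high-contrast, high-luminance charts reflect real-world demands, yet under the steps that is the only near chart test done with study lenses. The study used for the sample size covered near low-contrast acuity. It could therefore look as though a test the investigators wanted had been lost in drafting.

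**Working it through.** The plan gives no figure on this point, so the check compares the passages and counts tests.

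**Tests per outcome visit**

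| Source | Near high | Near low | Distance high | Distance low | Total |
|---|---|---|---|---|---|
| Table row, both contrasts at both distances | yes | yes | yes | yes | 2 × 2 = 4 |
| Table row, contrasts matched to distances in order | yes | no | no | yes | 2 |
| Visit 3 step 3 (and Visit 5) | yes | no | yes | yes | 2 + 1 = 3 |
| Primary endpoint plus third secondary endpoint | yes | no | yes | yes | 1 + 2 = 3 |

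The last two lines agree exactly. Only the table row differs.

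**How literally to take the row.** It packs two contrasts, two distances and two devices into one phrase. Crossed in full, that is 2 × 2 × 2 = 8 tests. The count of 4 arises only after each device is assigned to one distance (the app at 40 cm, E-ETDRS at 6 m), and that assignment comes from the endpoint list. If the endpoint list is also allowed to assign the contrasts, the count is 3, as in step 3. The table is a summary elsewhere too: it has no entry for manifest refraction, accommodation and binocular vision, or pupil size, and it shows no acuity at Visit 1. The Visit 1 steps include all of these.

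**Amount of data at issue.** With 35 completers and two outcome visits, the literal row gives 35 × 2 = 70 near low-contrast readings and the steps give 0. With all 39 enrolled the figures are 39 × 2 = 78 and 0.

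**Effect on listed endpoints.** Near high contrast, distance high contrast and distance low contrast appear both in the literal row and in step 3. MNREAD and NAVQ have their own rows and steps. No listed endpoint gains or loses an observation under either reading.

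**What adding the test would do.** The listed secondary comparisons number 4 (MNREAD) + 1 (NAVQ) + 2 (distance acuity) = 7; a near low-contrast endpoint makes 8. With no multiplicity adjustment, and assuming independence, the chance of at least one false positive goes from 1 − 0.95^7 = 0.302 to 1 − 0.95^8 = 0.337. Independence is only a convenience here, since four of the outcomes come from one MNREAD test. The rise is small, but it is a cost and not a correction.

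**The case for a change.** The best case for acting is that no natural reading of the row gives the three tests of step 3: it gives four or two. The row is therefore wrong as written. The sentence under the table, which says that assessments follow its sequence, gives the table some standing. Staff working from different pages could run the test in some participants or in one period only, which would spoil a paired comparison, and a missed reading cannot be recovered.

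The wording point stands. The rest carries less weight:

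- The sentence under the table concerns order, not content. At Visit 3 the table and the steps put NAVQ, acuity, MNREAD and slit lamp in the same order.
- Patchy collection would spoil only a measure that no endpoint uses.
- The Scientific Rationale never mentions low contrast. The remedy it names is digital real-world and patient-reported tools, and MNREAD and NAVQ are already secondary endpoints.
- The sample size text says what another study measured and likens this trial's primary endpoint to it. That primary endpoint is near high contrast. Likeness on the primary does not mean that every measure of the source was adopted.
- Adding the test would need a contrast level and an app able to show such a chart at 40 cm. The documents settle neither.

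**Conclusion.** The inconsistency exists, but it is clerical and calls for no change to the plan. Low contrast is confined to 6 m both in the visit steps and in the endpoint list, and one compressed table row departs from them. Tidying that row would alter no endpoint, sample size, analysis or conclusion. Analysts working from the endpoint list would reach the intended set of acuity outcomes without it.

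The stake is at most 70 readings among 35 completers on a measure attached to no endpoint; the effect on the primary and the seven listed secondary comparisons is nil. This rests on taking the agreement between step 3 and the endpoints as the intended design. If the sponsor did mean to test near low contrast, its absence from the endpoints would be a design choice, with MNREAD and NAVQ still covering near function, and any near low-contrast result would have to be reported as exploratory.
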